9.7.2. Azacitidine

Subcutaneous or IV azacitidine will be prepared and administered as detailed in Appendix 15.3.

Subjects will receive azacitidine 75 mg/m²/day SC or IV for 1 week every 4 weeks until the end of the study, unless they are discontinued from the treatment. A full 7 days of azacitidine is required, but as per institutional practice, a schedule of 5 days of daily dosing, followed by no dose received on the weekend, and 2 daily doses given again at the start of the next week, is allowed. The same schedule should be used for each subject throughout the duration of treatment, when possible.

In the event that 2 or fewer doses are missed during the 7-day dosing period, dosing should continue so that the subject receives the full 7 days of therapy. If 3 or more days are missed during the 7-day dosing period, the Investigator should contact the Medical Monitor, and a decision on dosing will be made on an individual case basis.

On days when both AG-120 or placebo and azacitidine are given, AG-120 or placebo will be given prior to azacitidine.

9.8. Criteria for Dose Escalation, Dose Modification, or Discontinuation of Study Drug

9.8.1. AG-120/Placebo Dose Modification and Stopping Criteria

Intra-subject dose escalation will not be permitted.

For any AE, including AEs not specifically mentioned in Table 1, the Investigator may decide to delay dosing or modify the dose of AG-120/placebo based on clinical judgment. All dose modifications of AG-120/placebo should be discussed with the Sponsor prior to implementation. Dose modifications of AG-120/placebo from 500 mg to 250 mg will be permitted on study for management of AEs (see Table 1). If more than 1 AE occurs that would require a dose modification, upon resolution of all AEs to baseline or Grade 1, AG-120/placebo should be dose-reduced to 250 mg. Subjects who have had their dose of AG-120/placebo reduced due to a Grade ≥ 3 AE will be permitted to re-escalate to 500 mg after discussion with the Sponsor's Medical Monitor.

Dose delays for reasons other than management of AEs are discouraged. Dose delays up to 28 days will be permitted at the discretion of the Investigator in consultation with the Medical Monitor for reasons including management of AEs and for mitigating circumstances (eg, planned procedures).

Azacitidine and AG120/placebo can be interrupted concurrently, or either agent alone, depending on the attribution to an AE by the Investigator. If azacitidine is permanently discontinued, treatment with AG-120/placebo may continue at the discretion of the Investigator and with the agreement of the Medical Monitor, provided that the subject is in CR or CRi (including CRp).

If a subject cannot resume AG-120/placebo within 28 days, the subject should be discontinued from study treatment if they have previously discontinued treatment with azacitidine. Other reasons for treatment termination are provided in Section 8.5. If AG-120 or placebo is discontinued, the subject will complete the EOT and Follow-up Visits, and will then enter EFS Follow-up (if the subject has not already experienced an EFS event [eg, treatment failure, relapse, or death]) and subsequent Survival Follow-up. If a dose is delayed, visit days (in cycles/days) will be paused until the next planned study visit (eg, if a dose is held on C3D1, the next scheduled visit when dosing begins again will become C3D1); disease response assessments should continue regardless of dose delays.

Table 1: Management of Adverse Events

Adverse Events (AEs)	Action
Grade 2 nausea or vomiting (related or unrelated)	
 • Consider holding dose of AG-120/placebo until resolution of AE to Grade <1 within 4 weeks (28 days) of supportive therapy. • Manage with supportive therapy according to the institutional standard of care. • Resume AG-120/placebo at same dose.
Grade 3 AEs (related, first event)	
 • Hold dose of AG-120/placebo until resolution to Grade <1 or baseline within 4 weeks of supportive therapy and then resume dose. • Manage with supportive therapy according to the institutional standard of care. • If the Grade 3 AE recurs (a second time), hold dose until resolution, and then reduce AG-120/placebo to 250 mg in consultation with the Medical Monitor. Re-escalation may be permitted after discussion with the Medical Monitor. • If the Grade 3 AE recurs (a third time) despite dose reduction of AG-120/placebo, then consider discontinuing AG-120/placebo in consultation with the Medical Monitor.
Grade 4 hematologic AEs (related, first event)	
 • Hold AG-120/placebo. • Manage with supportive therapy according to the institutional standard of care. • If the AE resolves to Grade \leq1 or baseline within 4 weeks, then restart AG-120/placebo dosing at 250 mg in consultation with the Medical Monitor. Re-escalation may be permitted after discussion with the Medical Monitor. • If the AE does not resolve to Grade \leq1 or baseline within 4 weeks, consider discontinuing study treatment in consultation with the Medical Monitor. • If the Grade 4 AE recurs (a second time), despite dose reduction, hold dose until resolution. AG-120/placebo should be discontinued in consultation with the Medical Monitor.
Grade 4 non-hematologic AE (related)	
 • Discontinue AG-120/placebo.

Refer to Section 9.9 for management of AESIs for AG-120.

If AG-120/placebo is discontinued, the subject may continue treatment with azacitidine on study.

If the Investigator suspects that a subject has PML, treatment with AG-120/placebo should be suspended until a diagnosis of PML has been ruled out.

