9.7. Study Drug Preparation and Administration

Subjects may not receive study treatment for each treatment cycle until all Day 1 procedures have been completed and all doses of study treatment from the prior treatment cycle have been accounted for, including the number of missed doses (where applicable). For females of reproductive potential, a serum β -hCG pregnancy test (sensitivity of at least 25 mIU/mL) must be performed at Screening within 72 hours prior to study treatment administration and be verified as negative.

The first day of study treatment dosing is considered Day 1 of a cycle.

Subjects will be monitored for hematologic toxicity and non-hematologic (if thought to be causally related) toxicity, with the NCI CTCAE version 4.03 used as a guide for the grading of severity (see Section 11.2). Dosing interruptions or delays or dose modifications may occur for managing toxicities and/or treatment response during study treatment (see Section 9.8).

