9.8.2.2. Azacitidine Dose Modifications due to Hematologic Toxicity

Treatment with azacitidine is associated with anemia, neutropenia, and thrombocytopenia, particularly during the first 2 cycles. Complete blood counts should be performed as specified in the Schedule of Assessments (Table 6), and as needed to monitor toxicity.

Recovery is defined as an increase of cell line(s) where hematologic toxicity was observed of at least half of the difference of nadir and the baseline count plus the nadir count (ie, blood count at recovery \geq Nadir Count + $(0.5 \times [\text{Baseline count} - \text{Nadir count}]$).

For example, if the baseline, pre-cycle neutrophil count is $500 \times 10^9/\text{L}$ and the Nadir count is $100 \times 10^9/\text{L}$, recovery is defined as: $\geq 100 + (0.5 [500 - 100])$, $\geq 300 \times 10^9/\text{L}$.

Subjects without reduced baseline blood counts (ie, WBC count $>3.0 \times 10^9/\text{L}$, ANC $>1.5 \times 10^9/\text{L}$, and platelets $>75.0 \times 10^9/\text{L}$) prior to first treatment:

If hematologic toxicity is observed following azacitidine treatment, the next cycle of azacitidine therapy should be delayed until the platelet count and the ANC have recovered. If recovery is achieved within 2 weeks (14 days), no dose adjustment is necessary. However, if recovery has not been achieved within 2 weeks, the azacitidine dose should be reduced according to Table 2. Following dose modifications, the cycle duration should return to 4 weeks (28 days). The reduced dose should be maintained during subsequent cycles that are given (unless toxicity develops). A flow diagram for the determination of azacitidine dose adjustment in subjects without reduced baseline blood counts is provided in Appendix 15.4.

Table 2: Hematologic Dose Reductions for Azacitidine Based on Absolute Neutrophil Count and Platelets

Nadir Counts		% Dose in the next course if recovery ^a is not achieved in next 2 weeks (14 days)
ANC ($\times 10^9/L$)	Platelets ($\times 10^9/L$)	
≤ 1.0	≤ 50	50%
> 1.0	> 50	100%

Abbreviations: ANC = absolute neutrophil count.

^a Recovery = counts \geq nadir count + $(0.5 \times [\text{baseline count} - \text{nadir count}])$.

Subjects with reduced baseline blood counts (ie, WBC count $\leq 3.0 \times 10^9/L$ or ANC $\leq 1.5 \times 10^9/L$ or platelets $\leq 75.0 \times 10^9/L$) prior to treatment:

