9.11. Duration of Subject Participation

9.11.1. Treatment Duration

Daily treatment with AG-120 + azacitidine or placebo + azacitidine will begin on the first day of Cycle 1. Subjects should be treated for a minimum of six 4-week (28-day) cycles of combination therapy. With Medical Monitor approval, subjects may continue to receive:

- AG-120 or placebo following discontinuation of azacitidine, provided that they are in CR or CRi (including CRp) and need to discontinue azacitidine due to protocol-specified azacitidine-related toxicity (eg, delayed bone marrow recovery), or
- Azacitidine following discontinuation of AG-120 or placebo, provided that they have not met the definition of disease relapse or progressive disease.

Subjects should continue to receive study treatment until disease relapse, disease progression, treatment failure, development of an unacceptable toxicity (AE), confirmed pregnancy, withdrawal by subject, protocol violation, death, or End of Study.

Subjects with a response less than CR at 24 weeks or beyond can continue on treatment if demonstrating treatment benefit, defined as any of the following: 1) Transfusion-independence while on study treatment; 2) ANC >500/ μ L; or 3) platelets >50,000/ μ L.

Following discontinuation of study drug, subjects are to attend a Follow-up Visit 4 weeks (28 days) after the last dose of study drug for final assessments. When study drug is withheld from a subject in order to resolve a toxicity and the subject does not subsequently restart

treatment, EOT is defined as the date when the study drug was first held. Subjects should proceed with EOT assessments, safety assessments, and EFS/Survival Follow-up. If the decision not to restart study treatment occurs outside of the 4-week Safety Follow-up window, the subject should proceed with EFS/Survival Follow-up.

All subjects who discontinue study treatment without experiencing any 1 of the following: death, disease relapse, treatment failure, or withdrawal of consent, will be followed every Day 1 (± 7 days) of Weeks 9, 17, 25, 33, 41, 53, and every 24 weeks thereafter for EFS until they experience treatment failure, relapse, death, withdraw from the study, or until the time when 173 EFS events have occurred or as deemed necessary by the IDMC.

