10. STUDY ASSESSMENTS

10.1. Schedule of Assessments

Table 6 provides the Schedule of Assessments for all subjects enrolled in the study, while Table 7 summarizes the PK sampling time points and Table 8 summarizes the PD sampling time points. A detailed description of study assessments follows these tables.

After providing written informed consent, subjects will undergo Screening evaluations. The Screening Visit is to be conducted within 4 weeks (28 days) prior to randomization; however, the IDH1m Prescreening can be conducted prior to the 28-day Screening window. All Screening procedures should be complete prior to first study drug administration. Subjects are to attend study center visits as outlined in the Schedule of Assessments (see Table 6).

Study center visits will be conducted on an outpatient basis whenever possible. Study visits should occur on the scheduled visit day; a ± 3 -day window (± 7 days for bone marrow aspirate/biopsy, peripheral blood sampling for IDH-mutated cells/leukemic blasts, and evaluation of disease status) is allowed to accommodate subjects' schedules. Bone marrow evaluations and peripheral blood counts for response assessments should be performed within 1 day of each other.

An EOT Visit will be conducted as soon as possible after discontinuing both (or the second discontinued treatment if the 2 study treatments are discontinued on different days) study treatments (within 1 week of the last dose of study drug); in addition, subjects are to attend a Follow-up Visit 4 weeks after the last dose of study drug for final assessments. If a subject's dose is held and it is subsequently decided to discontinue treatment, the EOT Visit should be conducted as soon as possible, but no later than 4 weeks after the last dose of study drug.

All subjects who discontinue study treatment without experiencing any 1 of the following: death, disease relapse, treatment failure, or withdrawal of consent, will be followed every Day 1 (± 7 days) of Weeks 9, 17, 25, 33, 41, 53, and every 24 weeks thereafter for EFS until they experience treatment failure, or relapse, or death, or withdrawal of consent, or until the time when 173 EFS events have occurred or as deemed necessary by the IDMC.

Once the study is unblinded, survival follow up will continue. All subjects who are alive after an EFS event will be contacted every 8 weeks for survival follow-up until death, withdrawal by subject, loss to follow-up, or when the Sponsor ends the study.

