Abbreviations: AE = adverse event; ALP = alkaline phosphatase; ALT = alanine aminotransferase; ANC = absolute neutrophil count; AST = aspartate aminotransferase; β -hCG = beta-human chorionic gonadotropin; BP = blood pressure; BSA = body surface area; BUN = blood urea nitrogen; C1D1 = Cycle 1, Day 1; CR = complete remission; D = Day; ECG = electrocardiogram; ECHO = echocardiogram; ECOG = Eastern Cooperative Oncology Group; eCRF = electronic case report form; EFS = event-free survival; EOT = End of Treatment; ICF = informed consent form; IDH = isocitrate dehydrogenase; IDH1 = isocitrate dehydrogenase 1; IV = intravenous; LVEF = left ventricular ejection fraction; MUGA = multi-gated acquisition; PD = pharmacodynamic; PK = pharmacokinetic; QD = once daily; RBC = red blood cell; SAE = serious adverse event; SC = subcutaneous; W = week; WBC = white blood cell.

* Subjects may sign a pre-Screening ICF to allow for collection of a bone marrow and peripheral blood sample for central IDH1 and [REDACTED] prior to the 4-week (28-day) Screening window. Bone marrow biopsy/aspirate and peripheral blood samples must be sent with proof of shipment to the central laboratory as part of Pre-screening to satisfy the Screening time points for these sample types, as long as they are collected within 28 days prior to randomization.

- 1 Screening assessments that may have been conducted prior to informed consent but within 28 days of C1D1 need not be repeated and results may be entered into the eCRF.
- 2 All subjects are to undergo an EOT assessment within 1 week of the last dose of study treatment (AG-120/placebo and azacitidine). If a subject discontinues study treatment at a regularly scheduled visit, EOT assessments may be performed at that visit. Subjects' eligibility to cross over to AG-120 + azacitidine after Sponsor unblinding of the study will be determined based on procedures conducted in the EOT Visit.
- 3 All subjects are to have a post-treatment visit 4 weeks (± 3 days) after the last dose of study treatment (AG-120/placebo and azacitidine).

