10.6.5. Safety Laboratory Assessments

Clinical laboratory evaluations are to be performed by the site's local laboratory. Prior to starting the study, the Investigator will provide to the Sponsor (or its designee) copies of all laboratory certifications and normal ranges for all laboratory parameters to be performed by that laboratory.

Clinical laboratory evaluations are to be conducted according to the Schedule of Assessments (6). In addition, all clinically significant laboratory values will be further investigated according to the judgment of the Investigator.

The following safety laboratory parameters are to be evaluated by the Investigator:

Hematology: Hemoglobin, RBC count, WBC count with differential, ANC, platelet count, peripheral blast count

Chemistry: Sodium, potassium, calcium, magnesium, albumin, glucose, BUN, creatinine, lactate dehydrogenase, ALP, AST, ALT, total bilirubin, phosphate, bicarbonate

Coagulation Studies: Activated partial thromboplastin time (aPTT), INR

Blood for hematology and chemistries is to be obtained: at Screening; on Days 1, 8, 15, and 22 (± 3 days) of Cycle 1 (Weeks 1, 2, 3, and 4); on Days 1 and 15 (± 3 days) of Cycles 2, 3, and 4 (Weeks 5, 7, 9, 11, 13, and 15); on Day 1 (± 3 days) of each treatment cycle thereafter (Weeks 17+); at EOT; and at 4 weeks post-treatment. All blood samples for hematology and chemistries must be drawn prior to administration of study drugs.

Blood for coagulation studies is to be obtained at Screening, on Day 1 (± 3 days) of each treatment cycle, and at the EOT Visit.

Pregnancy Test: All women of reproductive potential must have a negative pregnancy test to be eligible. A serum β -hCG pregnancy test will be performed at Screening and must be confirmed negative within 72 hours prior to study treatment administration.

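### Protocol Section 9.8.1 sends a subject who stops AG-120/placebo to EOT and EFS Follow-up without requiring that azacitidine has also stopped, contrary to Sections 9.11.1 and 10.1 and Table 6.

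*Protocol*

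**What the plan says.** **The rule in question.** Protocol Section 9.8.1, in the text before Table 1: "If AG-120 or placebo is discontinued, the subject will complete the EOT and Follow-up Visits, and will then enter EFS Follow-up". The sentence goes on to limit EFS Follow-up to subjects without a prior EFS event and to add Survival Follow-up. It does not mention azacitidine.

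**Azacitidine alone is allowed.** Below Table 1, the same section says: "If AG-120/placebo is discontinued, the subject may continue treatment with azacitidine on study". Section 9.11.1 lists, among treatments that may continue with Medical Monitor approval: "Azacitidine following discontinuation of AG-120 or placebo, provided that they have not met the definition of disease relapse or progressive disease".

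**When EOT occurs.** Section 10.1 places the EOT Visit after both drugs are stopped, "or the second discontinued treatment if the 2 study treatments are discontinued on different days". Table 6 footnote 2 puts the EOT assessment "within 1 week of the last dose of study treatment (AG-120/placebo and azacitidine"), and footnote 3 uses the same pairing for the 4-week visit. Section 7.1 joins the two drugs with 'or', and the Synopsis joins them with a plus sign.

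**How the SAP counts the time.** SAP Section 6.3.2 ends study treatment at the latest end date of any study drug. Section 6.3.5 extends the on-treatment period to 28 days after that.

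**The concern.** A subject who stops AG-120/placebo for toxicity and stays on azacitidine has two visit schedules. Section 9.8.1 read alone sends the subject to EOT, the Follow-up Visit and then EFS Follow-up. Section 10.1 and Table 6 keep the subject on the treatment schedule until azacitidine also stops.

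The choice affects safety monitoring. The EFS Follow-up column of Table 6 has no hematology, chemistry or ECG. A site following Section 9.8.1 to the letter would therefore have no scheduled blood counts, under that column, for a subject still receiving a myelosuppressive drug. The SAP would nevertheless treat that period as on-treatment in the laboratory and ECG summaries.

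**Working it through.** The plan gives no figure to reproduce here. The check is a comparison of texts followed by a visit count.

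**Step 1. Which rule is out of line?** For a subject who stops AG-120/placebo and continues azacitidine:

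| Source | Where it puts EOT |
|---|---|
| Protocol 9.8.1, disputed sentence | when AG-120/placebo stops |
| Protocol 10.1 | when the second drug stops |
| Table 6 footnotes 2 and 3 | last dose of AG-120/placebo and azacitidine |
| Protocol 7.1 | worded with 'or'; does not settle it |
| SAP 6.3.2 (end of study treatment) | latest end of either drug |

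Section 10.1 is the explicit rule for this case. The note to Table 7 points the same way: it provides for a single PK sample at a visit when study drug has been permanently discontinued, so such subjects are expected to attend treatment visits.

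**Step 2. What is scheduled on treatment?** Section 10.6.5 sets hematology and chemistry for Days 1 and 15 "of Cycles 2, 3, and 4 (Weeks 5, 7, 9, 11, 13, and 15"), then Day 1 of each cycle (Weeks 17, 21, 25). Section 10.6.4 sets ECGs at Weeks 5 and 7, then Day 1 of each cycle (Weeks 9, 13, 17, 21, 25). In Table 6, EOT has both, the 4-week visit has blood tests only, and EFS Follow-up has neither.

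**Step 3. What does Section 9.7 still require?** "Subjects may not receive study treatment for each treatment cycle until all Day 1 procedures have been completed". A subject receiving further azacitidine cycles therefore still has the Day 1 items. Coagulation tests, pregnancy tests and weight/body surface area are also absent from the EFS Follow-up column, but they too are Day 1 items.

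**Step 4. Count.** Assume AG-120/placebo stops at a Day 1 visit and azacitidine continues through Week 25. Count scheduled items after the 4-week visit. Uncovered = scheduled minus Day 1.

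| Stop | 4-week visit | Later draws | Of these, Day 1 | Uncovered draws | Later ECGs | Of these, Day 1 | Uncovered ECGs |
|---|---|---|---|---|---|---|---|
| Week 5 | Week 9 | 11, 13, 15, 17, 21, 25 (6) | 4 | 6 − 4 = 2 | 13, 17, 21, 25 (4) | 4 | 0 |
| Week 9 | Week 13 | 15, 17, 21, 25 (4) | 3 | 4 − 3 = 1 | 17, 21, 25 (3) | 3 | 0 |
| Week 13 | Week 17 | 21, 25 (2) | 2 | 0 | 21, 25 (2) | 2 | 0 |
| Week 17 | Week 21 | 25 (1) | 1 | 0 | 25 (1) | 1 | 0 |

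The starting point of the count matters slightly. Between the stop and the 4-week visit, the follow-up columns also lack one mid-cycle draw for a stop at Week 5, 9 or 13 (Week 7, 11 or 15 respectively), and the Week 7 ECG for a stop at Week 5. Counted from the stop itself, the uncovered draws are 2 + 1 = 3, 1 + 1 = 2, 0 + 1 = 1 and 0, and the uncovered ECGs are 1, 0, 0 and 0.

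**Step 5. Efficacy.** Protocol Section 12.5.1 and SAP Section 7.7.1.1 date a subject without CR by Week 24 at Day 1 of randomization, whichever visit schedule was used. Disease assessments continue on the same calendar in EFS Follow-up (Protocol Section 7.1). The primary EFS analysis does not change.

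**The case against.** The best defence is context. Two sentences earlier, Section 9.8.1 says that a subject who cannot resume AG-120/placebo within 28 days should leave study treatment if azacitidine has already been stopped. The next sentence refers to other reasons for ending treatment. On that reading the paragraph concerns the end of all treatment, and the disputed sentence says what follows. This is probably what was intended. However, the condition is not repeated, and the sentence opens with AG-120 or placebo alone.

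The second defence is that the answer is available elsewhere. Section 10.1 is explicit, the Table 6 footnotes agree, and azacitidine alone needs Medical Monitor approval under Section 9.11.1, so a site would not decide unaided. That lowers the chance of error but leaves the contradictory instruction in place.

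A reader might draw three stronger conclusions, none of which the documents support:

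- *Monitoring would lapse on azacitidine.* Section 9.7 requires Day 1 procedures. Section 9.8.2 calls for hematologic and renal monitoring. Section 9.8.2.2 says "Complete blood counts should be performed as specified in the Schedule of Assessments" and as needed to monitor toxicity. Sections 11.2 and 12.6.1 record and tabulate adverse events through 28 days after the last dose.
- *The primary result is at risk.* Step 5 shows that it is not.
- *EFS sensitivity analysis 5 has an ambiguous event date.* SAP Section 7.7.1.2 item 5 uses EOT without a cross-reference, but SAP Sections 6.3.1 and 6.3.2 supply the natural meaning. That is a missing pointer. Any effect on the result cannot be determined from the documents.

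**Conclusion.** The conflict is real and minor. Section 9.8.1 lacks a condition that its context implies and that Section 10.1 and Table 6 require. If the sentence is followed literally and Section 9.7 is observed, the gap after the 4-week visit is 2, 1, 0 or 0 mid-cycle blood draws and no ECGs. Including the four weeks before that visit adds at most one draw, plus one ECG for a stop at Week 5. These counts assume that AG-120/placebo stops at a Day 1 visit, that cycles stay on the 28-day calendar, and that azacitidine runs through Week 25. The documents do not show how many subjects would be affected. The change is worth making because it is cheap and concerns safety monitoring. It is not essential to the validity of the trial.

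**What to change.** 1. **Protocol Section 9.8.1.** Change the opening condition of the sentence to: *If both AG-120/placebo and azacitidine have been permanently discontinued*. Keep the rest as it stands, including the exception for subjects with a prior EFS event and the subsequent Survival Follow-up. Replacing the whole sentence would risk sending subjects who have already relapsed or failed treatment into EFS Follow-up.
2. **Same place, add:** *A subject who stops only AG-120/placebo and continues azacitidine stays on the treatment schedule in Table 6.*
3. **Protocol Section 7.1.** In the EOT sentence, change 'or' to 'and' between AG-120/placebo and azacitidine, to match Table 6 footnote 2.

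The cost is one amended condition, one added sentence and one changed word. No assessments are added to the existing treatment schedule, and the primary analysis, sample size and alpha do not change.
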